2 SPECIFIC AIMS

The primary objective of this cross-sectional epidemiologic study is to measure physician and patient awareness and understanding of the key messages in the prescriber guide and patient alert card.

Specifically, the following objectives will be addressed:

- Investigate whether physicians and their patients have received the educational materials.
- Assess knowledge and understanding among physicians regarding key safety information contained in the prescriber guide and assess how physicians use the materials in their daily practice.
- Assess knowledge and understanding of patients regarding the key safety information contained in the patient alert card and determine if the patients use and carry the patient alert card with them.

3 STUDY DESIGN

3.1 Physician Assessment

3.1.1 Physician Assessment Overview

A geographically dispersed and diverse set of physicians prescribing rivaroxaban in the UK, Germany, France, Italy, and Spain will be selected to reflect the distribution of physician specialities who prescribe rivaroxaban. Physicians will be asked to complete an online questionnaire evaluating their knowledge of key safety information as well as their receipt and use of the educational materials for rivaroxaban. Data will be analysed using descriptive tables summarising demographics, results, and other available characteristics. Timing and sequence of study initiation in each country will be determined based upon the product launch schedule and timing of ethics approval.

3.1.2 Physician Population and Eligibility

This cross-sectional study will be conducted in each of the five countries (the UK, Germany, France, Italy, and Spain) with distribution among a variety of physician specialties including, for example, general practitioners, cardiologists (office and hospital), haematologists, hospital stroke physicians, emergency care physicians, phlebologists, neurologists, angiologists, and other specialists in internal medicine (office and hospital). Representation by each physician group will reflect, to the extent possible, prescribing patterns in each country. Physicians will complete an online questionnaire eliciting information about their knowledge and use of the prescriber guide for rivaroxaban.

Physicians will be eligible to participate in this study provided they have prescribed rivaroxaban to at least one patient in the past 6 months for one of the following indications:

- Prevention of stroke and systemic embolism in adult patients with non-valvular atrial fibrillation (SPAF).
- Treatment of DVT and prevention of recurrent DVT and PE following an acute DVT in adults.

3.1.3 Physician Selection and Recruitment

The physician sampling frame will be constructed from a physician panel and/or prescriber list. The final frame will be determined with the objective of achieving a generally representative sample of physicians prescribing rivaroxaban. Geographic location, speciality, practice size, practice type, etc. will be taken into consideration. If the distribution of

physicians in the sampling frame appears consistent with the distribution believed in the targeted population, physicians will be randomly selected from the sample frame. However, if the distributions do not appear consistent with the targeted population, the sampling frame will be stratified by speciality and/or geography, and specific numbers of physicians within each stratum will be selected in order to recruit a sample that matches the distribution in the target population. In this case, the physician recruitment within each stratum will be done randomly. The final sampling strategy will be determined once rivaroxaban is on the market and will be designed to minimise bias and to allow for the study results to be generalised to the entire population of rivaroxaban prescribers to the extent feasible.

3.1.4 Physician Sample Size

The study will target 300 participating physicians per country, for a total of approximately 1,500 physicians overall¹, to allow reasonable precision around estimates of physicians' knowledge and understanding of the prescriber guide. For example, if we assume that the total sample of participating physicians can be treated as a simple random sample and that the percent of correct responses to a true/false question is 85%, then for a sample of size 300, the two-sided 95% confidence interval will be 80.4% to 88.8%. Table 1 shows the exact 95% confidence limits assuming various combinations of sample size and correct response percentages.

Table 1. Exact 95% Confidence Limits for Various Combinations of Sample Size and Correct Response Percentage

| Sample Size | Correct Response (%) | Lower 95% Confidence Limit (%) | Upper 95% Confidence Limit (%) |
|-------------|----------------------|--------------------------------|--------------------------------|
| 100 | 80 | 70.8 | 87.3 |
| 100 | 85 | 76.5 | 91.4 |
| 300 | 80 | 75.0 | 84.4 |
| 300 | 85 | 80.4 | 88.8 |
| 500 | 80 | 76.2 | 83.4 |
| 500 | 85 | 81.6 | 88.0 |
| 1,500 | 80 | 77.9 | 82.0 |
| 1,500 | 85 | 83.1 | 86.8 |

¹ Due to drug approval delays in Italy, the 18-month assessment will not include Italy. Therefore, the total sample size for the 18-month assessment will be 1,200 physicians.

3.1.5 Physician Questionnaire Development

Standard survey methodologic principles have been used to develop the physician questionnaire, which will assess physicians' knowledge of the following concepts as outlined in the prescriber guide and educational materials:

- Switching from or to rivaroxaban treatment
- Necessity of taking the 15-mg and 20-mg tablets with food
- Use of coagulation tests and their interpretation
- Dosing recommendations
- Perioperative management
- Populations at higher risk of bleeding
- Necessity of providing all patients with a patient alert card and counselling about the details of the patient alert card

Physicians will be asked about their receipt and use of the prescriber guide (Appendix A) as well as counselling of patients and distribution of the patient alert card. In addition, physicians will be asked to characterise their practice in terms of years in practice, size of practice, and history of treating patients with the diagnoses of interest. Other characteristics will be collected to facilitate stratified analyses to explore factors associated with knowledge and behaviour. The physician questionnaire is designed to take 10-15 minutes to complete. The physician questionnaire has been cognitively tested with physicians in each of the target countries. Section 3.3 provides a detailed description of the cognitive pretesting process. Modifications have been made to the questionnaire based on the pretesting results and additional feedback from the sponsor. The final version of the questionnaire can be found in Appendix C. Some modifications to the questionnaire are anticipated based on country-specific requirements.

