- Prevention of stroke and systemic embolism in adult patients with non-valvular atrial fibrillation with one or more risk factors, such as congestive heart failure, hypertension, aged ≥ 75 years, diabetes mellitus, and prior stroke or transient ischaemic attack.
- Treatment of DVT and prevention of recurrent DVT and PE following an acute DVT in adults.

As a part of this safety risk management plan revision, a physician educational pack has been developed that includes the summary of product characteristics, prescriber guide (Appendix A), and patient alert card (Appendix B), with the aim to increase awareness and understanding among physicians and patients about the potential bleeding risk during treatment with rivaroxaban.

The prescriber guide covers the following topics:

- Switching from or to rivaroxaban treatment
- Necessity of taking the 15-mg and 20-mg tablets with food
- Management of overdose situations
- Use of coagulation tests and their interpretation
- Dosing recommendations
- Perioperative management
- Populations at higher risk of bleeding
- Necessity of providing all patients with a patient alert card and counselling about the details of the patient alert card

The patient alert card contains the following key safety messages:

- Signs or symptoms of bleeding and when to seek attention from a health care provider
- Importance of treatment compliance
- Necessity of taking the 15-mg and 20-mg tablets with food
- Necessity of carrying the patient alert card with them at all times
- Necessity of informing health care professionals (HCPs) that they are taking rivaroxaban if they need to have any surgery or invasive procedure

This protocol describes the planned evaluation of these elements of the risk management plan. Evaluations are planned for administration at 18 months, 3 years, and 7 years post-launch. The status of these assessments will be presented regularly in periodic safety update reports. The five countries to be included in the study are the United Kingdom (UK), Germany, France, Italy, and Spain. Due to drug approval delays in Italy, the 18-month assessment will not include Italy. Therefore, data will be collected from four countries in the 18-month assessment (UK, Germany, France, and Spain).

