Several sub-groups of patients are at increased risk of bleeding and should be carefully monitored for signs and symptoms of bleeding complications.

Treatment decision in these patients should be done after assessment of treatment benefit against the risk of bleeding.

- **Patients with renal impairment:** See “dosing recommendations” for patients with moderate (creatinine clearance 30-49 ml/min) or severe (15-29 ml/min) renal impairment. Use of Xarelto is not recommended in patients with creatinine clearance <15 ml/min.
- **Patients concomitantly receiving other medicinal products:**
 - Use of Xarelto is not recommended with systemic azole-antimycotics (such as ketoconazole, itraconazole, voriconazole and posaconazole) or HIV protease inhibitors (e.g. ritonavir).
 - Take care with drugs affecting haemostasis such as NSAIDs, acetylsalicylic acid, or platelet aggregation inhibitors.

- ***Patients with other haemorrhagic risk factors:***

As with other antithrombotics, Xarelto is not recommended in patients with an increased bleeding risk such as:

- congenital or acquired bleeding disorders
- uncontrolled severe arterial hypertension
- other gastrointestinal disease that can potentially lead to bleeding complications
- vascular retinopathy
- bronchiectasis or history of pulmonary bleeding

PERIOPERATIVE MANAGEMENT

If an invasive procedure or surgical intervention is required, Xarelto 15/20mg should be stopped at least 24 hours before the intervention if possible, and based on the clinical judgement of the physician. If the procedure cannot be delayed the increased risk of bleeding due to Xarelto should be assessed against the urgency of the intervention.

Xarelto should be restarted as soon as possible after the invasive procedure or surgical intervention provided the clinical situation allows and adequate haemostasis has been established.

OVERDOSE

Due to limited absorption a ceiling effect with no further increase in average plasma exposure is expected at supratherapeutic doses of 50mg Xarelto and above. The use of activated charcoal to reduce absorption in case of overdose may be considered.

HOW TO MANAGE BLEEDING COMPLICATIONS

Should bleeding complications arise in a patient receiving Xarelto, the next Xarelto administration should be delayed or treatment discontinued as appropriate. Individualised bleeding management may include:

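### Overdose management is listed as a prescriber-guide topic but appears neither in the section 3.1.5 concepts nor in any Appendix C item, so the study yields no physician data on it

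*Protocol*

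**What the plan says.** **Scope.** Protocol section 1 (Background) lists eight topics covered by the prescriber guide. The third is "Management of overdose situations". After the guide and alert-card lists it states: "This protocol describes the planned evaluation of these elements of the risk management plan". No topic is excepted.

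**Objectives.** Section 2 sets the primary objective as to "measure physician and patient awareness and understanding of the key messages in the prescriber guide and patient alert card". A specific physician objective follows: "Assess knowledge and understanding among physicians regarding key safety information contained in the prescriber guide".

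**Questionnaire.** Section 3.1.5 says the physician questionnaire will assess "knowledge of the following concepts as outlined in the prescriber guide and educational materials" and lists seven concepts. Overdose is not one of them. The same section fixes the instrument: "The final version of the questionnaire can be found in Appendix C". The introduction to Appendix C tells physicians that the assessment will show whether the educational materials, the prescriber guide included, are correctly understood.

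**The guide.** Appendix A names overdose in its contents list and gives it a section of two sentences. One begins "Due to limited absorption a ceiling effect with no further increase in average plasma exposure is expected"; the other reads "The use of activated charcoal to reduce absorption in case of overdose may be considered". The guide's section on coagulation testing also names overdose as one of the exceptional situations in which measuring drug levels may be useful.

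**The concern.** The section 3.1.5 list follows the section 1 list in the same order, with one line missing. Nothing in section 3.1.5, or in the strengths and limitations in section 5, says that overdose was left out on purpose. A reader of sections 1 and 2 would expect a result for every listed guide topic, and for this one there can be none.

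What is at stake is the scope of the conclusion. The study is a regulatory commitment. Its report could state that physicians understand the guide, on the strength of a target of 1,200 physicians at 18 months and about 1,500 when all five countries take part, without a single response on overdose. Unless the report says so, the reader cannot tell that one topic was not measured. Statistical precision is not the issue: no sample size helps a question that is not asked.

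**Working it through.** No formula applies and the protocol gives no figure to reproduce. The check sets the section 1 topic list against the section 3.1.5 concept list and against every item in Appendix C. The assignment of items to topics is mine, from their content.

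| Guide topic in section 1 | In section 3.1.5? | Items in Appendix C |
|---|---|---|
| Switching to or from the drug | Yes | Q10–Q13 |
| Taking the 15 mg and 20 mg tablets with food | Yes | Q8 |
| Overdose | **No** | **None** |
| Coagulation tests | Yes | Q9, Q10 |
| Dosing | Yes | Q16–Q18 |
| Perioperative management | Yes | Q14 |
| Groups at higher bleeding risk | Yes | Q6, Q7 |
| Alert card and counselling | Yes | Q21–Q23 |

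1. **Lists.** Section 1 has 8 topics and section 3.1.5 has 7. 8 − 7 = 1, and the one missing is overdose.

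2. **Items in the table.** Q6–Q14 (9 items), Q16–Q18 (3) and Q21–Q23 (3) make 15.

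3. **Remaining items.** Q1–Q4 cover prescribing history and role (4), Q5 the most important risk (1), Q15 bleeding complications (1), Q19–Q20 information sources and their helpfulness (2), and Q24–Q27 physician and practice characteristics (4), making 12. 15 + 12 = 27, so every numbered item is accounted for. None concerns overdose, and neither does the screening question S1.

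4. **Nearest item.** Q15 asks what to do for a medically important bleeding complication. Its options are symptomatic treatment, delaying or stopping the drug, haemodynamic support, a procoagulant reversal agent and referral to emergency care. They correspond to the guide's separate section on bleeding complications, apart from referral. None reflects either sentence of the overdose section.

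5. **Other routes to the data.** Q9 and Q10 ask about routine coagulation monitoring and about INR monitoring, not about measuring drug levels after an overdose. Section 3.1.5 anticipates country-specific changes to the questionnaire, but none is said to add overdose.

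**The case against.** The best defence is that section 1 does not promise coverage topic by topic. On this view the elements it mentions are the tools of the educational pack (product summary, guide and card) rather than each bullet. Section 1 calls the guide's contents topics and reserves the phrase about key safety messages for the card, so the objective in section 2 need not extend to every guide topic. Section 3.1.5 is the operative section, it agrees with Appendix C, and choosing a subset of the guide for a 10–15 minute survey is a legitimate design choice. The section 1 list is not an exact inventory of the guide either: it omits bleeding complications, which Q15 nevertheless tests. Finally, the pack's stated aim concerns bleeding risk, and the overdose section is short and partly permissive, so it is not easy to turn into a right-or-wrong question.

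Much of this stands. The protocol does not itemise the guide's key messages, the sentence about elements can be read either way, and the omission may be deliberate. The practical loss is limited.

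It does not remove the mismatch. Even if the elements are the tools, the section 2 objectives and the Appendix C introduction speak of the guide without exception, and nothing tells the reader that one topic is left out. Section 1 is the nearest thing to an itemisation, and section 3.1.5 adopts it for the other seven topics. If the choice was deliberate, the stated scope should be narrowed to match.

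Two stronger readings should be resisted:

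- A reader might count no overdose item among the 14 knowledge items Q5–Q18 and treat that as singling overdose out. It does not: the alert-card topic also lies outside that range, in Q21–Q23. The count that does distinguish overdose is none in Q1–Q27.
- A reader might infer that poor understanding of this topic would go unnoticed at 18 months, 3 years and 7 years. That assumes the same questionnaire throughout. The protocol calls Appendix C final but does not say that it is frozen for the later assessments.

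**Conclusion.** The point holds as a gap in content coverage. One of eight listed guide topics is absent from the questionnaire concepts without explanation and has no item among Q1–Q27 or in S1. For any assessment that uses Appendix C as it stands, there will be no physician data on overdose management.

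It would be too strong to say that the primary objective goes unanswered, or that a named risk is missed. Overdose is listed as a guide topic, not as a risk, and the objective is affected for that topic alone. Nor should one topic in eight be read as a fraction of the objective lost, since the protocol gives no weights to the topics.

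The conclusion rests on Appendix C being the fielded instrument, as section 3.1.5 states, and on no country version adding the topic. It does not depend on how the data will be analysed.

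**What to change.** Sections 1, 2 and 3.1.5 and Appendix C should be reconciled in one of two ways.

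1. **Measure the topic.** Restore overdose management to the concept list in section 3.1.5 and add one closed-ended question to Appendix C. Key it only to what the guide's overdose paragraph already says, with at least one incorrect option and a don't-know option. The cost is one more question in a 10–15 minute survey, its translation and a brief wording check, because the item will have missed the completed cognitive pretest.

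2. **Narrow the scope.** If the omission is intended, say so with the reason in sections 1, 2 and 3.1.5, and state in the report that overdose management was not evaluated. Conclusions about understanding of the guide should then exclude it. The cost is a few sentences.

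For any assessment already fielded, only the second course is available.

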 **Xarelto**
rivaroxaban

Prescribing Information can be found on pages 10 and 11

211 mm

DO NOT PRINT GUIDES

297 mm

Bayer HealthCare have designed this educational pack to support you in the appropriate prescribing of Xarelto. It contains important information specifically relating to 15mg and 20mg dosing of Xarelto, for use in stroke prevention in AF and treatment of DVT and PE.

Within this pack you will find a:

- Prescriber guide
- Summary of product characteristics (SmPC)
- Patient alert card

If you would like to order more copies of the Xarelto educational pack, please visit www.xarelto-info.co.uk

Alternatively, please contact Bayer Medical Information at [contact] or call [name].

DO NOT PRINT GUIDES

211 mm

**NOW UPDATED
AND INCLUDES A
NEW INDICATION**

XARELTO® (RIVAROXABAN)

PRESCRIBER GUIDE

FOR 15MG AND 20MG DOSING

Prescribing information can be found
on pages 10 and 11

This guide is to be used to support the appropriate use of Xarelto in eligible atrial fibrillation (AF) patients and for the treatment of deep vein thrombosis (DVT) and pulmonary embolism (PE).

It includes the following information:

- **Indications**
- **Dosing recommendations**
- **Populations potentially at higher risk of bleeding**
- **Perioperative management**
- **Overdose**
- **How to manage bleeding complications**
- **Coagulation testing**

Xarelto patient alert card

You must provide a patient alert card to each patient who is prescribed Xarelto 15mg or 20mg.

Please explain the implications of anticoagulant treatment to patients, in particular highlighting the need for:

- treatment compliance
- taking medication with food
- signs or symptoms of bleeding
- when to seek medical attention.

The patient alert card will inform treating physicians and dentists about the patient's anticoagulation treatment and will contain emergency contact information.

Please instruct patients to carry the patient alert card with them at all times and present it to every health care provider.

INDICATIONS

Prevention of stroke and systemic embolism in adult patients with non-valvular AF with one or more risk factors, such as congestive heart failure, hypertension, age \geq 75 years, diabetes mellitus, prior stroke or transient ischaemic attack.

Treatment of DVT and PE and prevention of recurrent DVT and PE in adults. (See section 4.4 of the SmPC for haemodynamically unstable PE patients).

DOSING RECOMMENDATIONS

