| Xarelto Prescriber Guide |  |  |  |  |  |
| Briefing from a company representative |  |  |  |  |  |
| Discussion with a clinical expert |  |  |  |  |  |
| Summary of Product Characteristics |  |  |  |  |  |
| Medical Publications |  |  |  |  |  |
| Other |  |  |  |  |  |

Q21. Have you received Xarelto Patient Alert Cards to provide to your patients?

- Yes
- No

[IF Q21 IS NO, SKIP TO Q23.]

Q22. Considering the Xarelto patients under your care, to how many did you provide a Patient Alert Card?

- Every one of my patients
- Most of my patients
- A few of my patients
- None of my patients

Q23. When would you discuss the information on the Patient Alert Card with your patients taking Xarelto?

(Tick all that apply.)

- When first prescribing Xarelto
- When a patient is facing an invasive procedure or surgical intervention
- When a patient has bleeding complications
- When a patient has a Xarelto related adverse event
- I do not use the Patient Alert Card
- Other

In this next section, please tell us a little about yourself and your clinical practice.

Q24. Which of the following best describes your specialty?

- General medicine
- Neurology
- Cardiology
- Haematology
- Accident & Emergency medicine
- Oncology
- Other

Q25. How many years have you been practicing medicine?

- 5 years or less
- 6 to 10 years
- 11 to 15 years
- 16 to 20 years
- 21 to 25 years
- More than 25 years

Q26. Are you...?

- Male
- Female

Q27. How would you characterise your practice?

(Tick all that apply.)

- General practice
- Hospital-based clinic
- Nursing home
- Other

0302949 Physician Questionnaire

Thank you for completing the questionnaire!

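### Physicians' knowledge that every patient must be given, and counselled on, an alert card is listed as an assessed concept, but Appendix C has only receipt, distribution and timing items for it

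*Protocol*

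**What the plan says.** Section 3.1.5 introduces the physician questionnaire as one "which will assess physicians' knowledge of the following concepts as outlined in the prescriber guide and educational materials" and then gives seven concepts. The seventh is "Necessity of providing all patients with a patient alert card and counselling about the details of the patient alert card". The next paragraph adds, as a separate matter, that physicians will be asked about receiving and using the guide, "as well as counselling of patients and distribution of the patient alert card". Knowledge and practice are therefore both promised for this message. Section 2 makes the same distinction: one aim covers both what physicians know and how they use the materials in daily practice.

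The rule itself is in the Prescriber Guide (Appendix A): "You must provide a patient alert card to each patient who is prescribed Xarelto 15mg or 20mg". The guide also names the topics to explain to patients.

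On the instrument, section 3.1.5 states: "The final version of the questionnaire can be found in Appendix C". It anticipates some country-specific changes. In Appendix C the card appears in three items:

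- Q21: "Have you received Xarelto Patient Alert Cards to provide to your patients", answered yes or no, followed by the routing rule "IF Q21 IS NO, SKIP TO Q23".
- Q22: "Considering the Xarelto patients under your care, to how many did you provide a Patient Alert Card", with answers running from every patient to none.
- Q23: when the physician would discuss the card's information, with an option for those who do not use the card.

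**The concern.** A concept listed for knowledge assessment needs at least one item that can be scored against the educational material. For this concept there appears to be none.

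This is also the physician message most directly tied to the patient component. Section 2 asks whether patients received the materials, and patient Questionnaire #2 measures card receipt at Q10 (Appendix D). Sections 3.2.1, 4 and 5 envisage looking at patient results by the knowledge of their physician. If few patients report having a card, the sponsor will want to know whether physicians were unaware of the requirement, which points to the education, or were aware and did not act, which points to practice. An analysis plan cannot recover an answer that was never collected. With assessments planned at 18 months, 3 years and 7 years (section 1), the gap would recur each time unless the questionnaire changes.

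**Working it through.** No sample-size or error-rate arithmetic applies. The check maps the section 3.1.5 concept list onto Appendix C and then follows the routing.

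**Step 1: concepts against knowledge items.** The knowledge block runs from Q5 to Q18, which is 18 − 5 + 1 = 14 items.

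| Concept in section 3.1.5 | Items that can be scored against the guide |
|---|---|
| Switching to or from rivaroxaban | Q11, Q12, Q13 |
| Taking 15 mg and 20 mg with food | Q8 |
| Coagulation tests | Q9, Q10 |
| Dosing | Q16, Q17, Q18 |
| Perioperative management | Q14 |
| Populations at higher bleeding risk | Q6, Q7 |
| Card for all patients, with counselling | none |

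The two remaining items, Q5 (main risk) and Q15 (managing a bleed), do not mention the card. So 0 of 14 knowledge items address the seventh concept, and 6 of 7 concepts are covered.

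**Step 2: can Q21 to Q23 stand in?**

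- Q21 records supply. It says nothing about knowledge.
- Q22 records past behaviour. A physician may know the rule and not follow it, or give cards to everyone without knowing that this is required.
- Q23 concerns the timing of discussion. The guide's card section says what to explain and that each patient must have a card, but it gives no timing that would make one Q23 answer correct. Q23 does not ask whether counselling is required for all patients, and it has no don't-know option.

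**Step 3: the routing.**

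| Q21 answer | Items then asked | What can be learned | What cannot |
|---|---|---|---|
| Yes | Q22, Q23 | Extent of distribution; timing of discussion | Whether incomplete distribution reflects not knowing the rule or not acting on it |
| No | Q23 | That supply failed; timing of discussion | Whether the physician knows the rule |

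The skip omits one of the three card items (Q22) and lands on Q23, so every physician answers Q21 and Q23.

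**Step 4: size.** The number of physicians with a knowledge result on this concept is 0 of the 1,500 targeted overall, and 0 of the 1,200 targeted at the 18-month assessment. This does not depend on how Q21 is answered.

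**The case against.** The strongest reply is that this is a labelling slip. The protocol says it will ask about counselling and card distribution, and Q21 to Q23 do so. Q22 even has an answer that matches the guide, namely every patient, so it measures compliance, and use in daily practice is a stated aim. The patient side adds Q10 (card received) and Q15 (who explained it). On this view the remedy is to move one bullet from the knowledge list to the practice sentence.

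Much of that stands. Practice is covered, supply failure is identifiable from Q21, and moving the bullet is an acceptable fallback. But compliance is not knowledge, and section 3.1.5 promises both. The patient items show whether a card arrived and was explained, not why it did not.

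Two stronger readings are tempting and are not supported:

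- A reader might infer that physicians without cards are routed past the only question on the subject. They are not: the skip lands on Q23, which concerns counselling and goes to everyone. Skipping Q22 is sensible routing, since a physician who received no cards cannot usefully report how many were handed out. Nor do the documents show that such physicians are the least likely to know the rule. They may have learned it from the guide, receipt of which Q19 records separately.
- A reader might want to put a number on the physicians who miss Q22. The protocol gives no expected rate of No at Q21, so any count would rest on an invented figure. The gap does not need one.

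**Conclusion.** The point holds in a limited form. Appendix C yields no estimate of physicians' knowledge that all patients must be given, and counselled on, the card, although section 3.1.5 lists this among the seven concepts to be assessed. The study can identify physicians who lack cards. It cannot separate ignorance of the requirement from failure to act among those who have them, and it has no measure of knowledge among those who do not.

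The other six concepts and the practice measures are unaffected. The conclusion rests on Appendix C being the fielded instrument, as section 3.1.5 says. A country-specific modification that added such an item would close the gap in that country only.

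**What to change.** Add one keyed item to the knowledge block, before Q19, shown to every physician whatever the answer to Q21. It should ask which patients prescribed Xarelto 15 mg or 20 mg the Prescriber Guide says should be given, and counselled on, the alert card, with answers covering all patients, selected groups, none, and don't know. Keep Q21 to Q23 as supply and practice items. A further item on which topics the guide asks physicians to explain is optional.

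The cost is small but goes beyond respondent time: translation, brief pretesting and ethics notification for one item. Section 3.1.6 bars going back to change answers, so Q21 to Q23 cannot cue the new item. The reverse is possible: asking about the rule first may prime more favourable answers to Q22, and this should be noted when Q22 is interpreted.

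If the item is not added, move the concept from the knowledge list to the practice sentence in section 3.1.5 and state that knowledge of it is not measured.
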